#### **6.4. Baseline and Other Summaries and Analyses**

##### **6.4.1. Baseline Summaries**

The number and percentage of subjects with baseline serostatus of toxin A+/toxin B+, toxin A-/toxin B-, toxin A+/toxin B-, and toxin A-/toxin B+ will be provided and included in a subject demographic summary table.

## **6.4.2. Study Conduct**

### **6.4.2.1. Subject Disposition, Vaccination Administration, Blood Samples, and Screen Failures**

The number and percentage of subjects who are randomized will be included in the subject disposition summary for the originally planned stage: subjects who withdraw during the vaccination phase (Visit 1 to Visit 4 on the Day 1, 8 and 30 regimen; Visit 1 to Visit 5 on the Month 0, 1, and 6 regimen), complete the vaccination phase, , and withdraw after the vaccination phase will be summarized. The number and percentage of subjects who are re randomized will be included in the subject disposition summary for the extension stage: the number and percentage of subjects who complete the study and withdraw after fourth vaccination will be summarized. The reasons for withdrawal will also be tabulated. The reasons for withdrawal will be those specified in the database; no rewording/recoding will be done.

Subjects excluded from the evaluable immunogenicity population will also be summarized with reasons for exclusion.

The number and percentage of subjects randomized, vaccinated, and providing blood samples within the protocol-specified time frame, as well as before and after the specified time frame, will be tabulated for the originally planned stage. In addition, the number and percentage of subjects rerandomized, vaccinated, and providing blood samples within the protocol-specified time frame, as well as before and after the specified time frame, will be tabulated for the extension stage.

A listing of noncompliant vaccine administration will be provided. The protocol deviations will also be listed. Subjects who do not receive the vaccine as randomized will be listed as well. A listing of subjects who withdrew because of AEs will be provided.

All randomized subjects will be used to generate these tables. All of the summary tables will be presented for each vaccine group and for the total, separately for each assigned 3-dose regimen in the originally planned stage and the extension stage.

Subjects who sign the ICD but are screen failures will be also summarized separately for each assigned 3-dose regimen in the originally planned stage.

### **6.4.2.2. Demographic, Medical History, and Baseline Characteristics**

Descriptive summary reports for demographic characteristics will be provided for each vaccine group, separately for each regimen in the originally planned stage for the evaluable immunogenicity and mITT analysis populations.

Descriptive summary reports for medical history will be provided for each vaccine group, separately for each regimen for the safety population only in the originally planned stage.

#### **6.4.2.3. E-Diary Completion**

Variables defined in [Section 3.6.1](#) will be summarized with descriptive statistics for each vaccine group and for the total after each dose, separately for each regimen in the originally planned stage and the extension stage. The safety population will be used to generate this table.

#### **6.4.3. Analyses of Below LLOQ**

A table summarizing the number of subjects with assay data below the LLOQ will be produced for each vaccine group separately for each regimen in the originally planned stage and the extension stage. This table will be generated for both the evaluable and mITT immunogenicity populations.

### **6.5. Safety Summaries and Analyses**

All safety analyses will be summarized based on the safety population in accordance with Pfizer reporting standards. All safety summaries will be provided by vaccine group separately for each dose in each 3-dose regimen (Days 1, 8, and 30 and Months 0, 1, and 6) in the originally planned stage and for each original assigned regimen in the extension stage.

#### **6.5.1. Adverse Events**

It should be recognized that most studies are not designed to reliably demonstrate a causal relationship between the use of a pharmaceutical product and an AE or a group of AEs. Except for select events in unique situations, studies do not employ formal adjudication procedures for the purpose of event classification. As such, safety analysis is generally considered as an exploratory analysis and its purpose is to generate hypotheses for further investigation. The 3-tier approach facilitates this exploratory analysis. There will be no adjustment for multiple comparisons in the analyses.

For tier 1 and tier 2 events, the proportion of AEs observed in each vaccine group will be presented along with the point estimates and associated 95% CIs of the risk difference (the difference of incidence rates) between each vaccine and placebo.

For tier 1 events, 95% CIs will be calculated using the exact methods proposed by Chan and Zhang described in [Section 5.2.1](#).

For tier 2 events, 95% CIs will be calculated using the Miettinen and Nurminen method described in [Section 5.2.1](#).

For tier 1 events, p-values from Chan and Zhang's method will be calculated and included in the presentations. AEs will be arranged in the output sorted in descending order of point estimates of the risk difference (the difference of incidence rates) within system organ class.

### **6.5.2. Reactogenicity Data**

The derived endpoints ([Section 3.5.3](#)) for each local reaction, systemic event, and use of antipyretics/pain medication to treat symptoms will be summarized.

The presence and maximum severity of the local reaction and systemic event at “any day (Day 1 – Day 7)” following the first vaccination on the Day 1, 8, and 30 regimen “any day (Day 1 – Day 14)” following the second and third vaccinations on the Day 1, 8, and 30 regimen, and “any day (Day 1 – Day 14)” following each vaccination on the Month 0, 1 and 6 regimen in originally planned stage and fourth vaccination in the extension stage for both regimens will be summarized with 95% Clopper-Pearson CIs.

The presence of each local reaction and systemic event on any day (Day 1- X), any local reaction on any day (1-X), maximum severity of each local reaction and systemic event on any day (Day 1-X) following **any** vaccination on the Day 1, 8, and 30 regimen and the Month 0, 1, and 6 regimen in the originally planned stage will also be summarized with Clopper-Pearson CIs, where X = 7 days after the first vaccination on the Day 1, 8 and 30 regimen, and X = 14 after all other vaccinations in both regimens. For local reactions, systemic events, and use of antipyretic/pain medication to treat symptoms, descriptive summary statistics of the maximum duration of the event will be provided.

For the onset of local reactions, systemic events, and use of antipyretic/pain medication to treat symptoms, descriptive summary statistics of the onset day will be provided.

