The analysis of immunogenicity demonstrated a limited antibody response after Dose 1, but after Dose 2 there were marked increases in antibody titers against both toxin A and toxin B, which were generally maximal 7 days after Dose 2 and stable 1 month after Dose 2. Seven days after Dose 3, a substantial booster response was evident, which was slightly more marked again 1 month after Dose 3. Overall, robust antitoxin neutralizing responses were elicited by both formulations, although there was a trend for greater responses in recipients of the toxoid-alone formulation. With respect to the dose level, because of the limited sample size, 95% confidence intervals (CIs) were often overlapping for all 3 dose levels, indicating that it was not possible to discern a clear dose response.

In light of these results, a Phase 2 Study (B5091003) was designed to evaluate the safety, tolerability, and immunogenicity of the 100- and 200- $\mu$ g antigen dose levels of the toxoid-alone formulation in a 3-dose regimen administered at Days 1, 8, and 30 in healthy adults 50 to 85 years of age. Vaccinations in this study were stopped following the occurrence of 7 cases of Grade 3 injection site erythema among 162 subjects receiving the second vaccination at Day 8. Among the recipients of the active vaccine, this corresponded to an incidence of 5.0% (95% CI 2.1% to 10.1%). There were no accompanying severe systemic symptoms in the subjects, there was no report that the redness impacted their daily activities, and all local reactions fully resolved.

The local reactogenicity observed with the toxoid-alone formulation may have been due to free toxoid interacting with the elicited immune response. Since adsorption onto aluminum has been shown to bind and slowly release the vaccine constituents from the injection site, and reflecting the potential need for rapid induction of immune response and prolonged duration of protection, Study B5091009 will evaluate the safety, tolerability, and immunogenicity of 2 antigen dose levels of the aluminum hydroxide-containing vaccine (ie, 100  $\mu$ g and 200  $\mu$ g) in 2 different dosing regimens: Days 1, 8, and 30 or Months 0, 1, and 6. The primary immunogenicity endpoint will be assessed based upon a specified threshold estimate for each *C difficile* vaccine toxoid. The specified thresholds for each toxoid are considered to indicate protective titers.

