### **1.2.3. *Clostridium difficile* Vaccine Candidate**

Pfizer's vaccine candidate consists of a mixture of genetically modified *C difficile* toxoids A and B that are further chemically inactivated to eliminate residual cytotoxicity but retain native antigenic structure. In preclinical experiments, Pfizer's vaccine candidate was studied either alone or in combination with an adjuvant. In the hamster disease model, all vaccine formulations demonstrated a survival benefit, providing at least 90% protection from a lethal challenge with *C difficile* spores in the immunized hamsters. In nonhuman primates (NHPs), all of Pfizer's toxoid vaccine formulations tested induced robust neutralizing antitoxin antibody responses to both TcdA and TcdB.

Pfizer's *C difficile* vaccine candidate was assessed in a Phase 1 study (B5091001), conducted in the United States, where 192 healthy adults aged 50 to 85 years were enrolled. This first-in-human (FIH) study was a dose-escalating, placebo-controlled, randomized, observer-blinded trial to evaluate the safety, tolerability, and immunogenicity of *C difficile* vaccine, as a 3-dose regimen at Months 0, 1, and 6. Three antigen dose levels (50, 100, and 200 µg) of the vaccine candidate were assessed either alone or in combination with aluminum hydroxide.

The analysis of safety demonstrated that both formulations and all 3 dose levels were generally well tolerated. Local reactions were predominantly mild or moderate and comprised mostly injection site pain. No actual severe or Grade 4 local reactions were reported. In the 65- to 85-year age cohort, at the 200-µg dose level, local reactions tended to occur more frequently in the toxoid-alone compared to the aluminum hydroxide-containing dose groups (41.7%, 50.0%, and 80.0% versus 16.7%, 18.2%, and 11.1%, for any local

reaction after each of the 3 doses, respectively). After all 3 doses, the frequency and severity of local reactions did not increase with increasing dose level or number of doses for any of the dose groups. Systemic events were predominantly mild to moderate and comprised mostly headache and fatigue. There was no evidence of increased frequency of systemic events with increasing dose level or number of doses for any of the dose groups.

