#### **6.1.2. Visit 2: Day 8 - Vaccination 2 (7 to 11 Days After Visit 1)**

- Review the subject's e-diary data and follow up on any ongoing local reactions or systemic events.
- Ensure that the subject continues to be eligible for the study and does not meet any of the withdrawal criteria as described in [Section 6.5](#).
- Based on clinical evaluation, determine whether any AEs or SAEs have occurred since the last study visit. Record and report findings as described in [Section 8](#) and the [Schedule of Activities](#). Review AEs that were ongoing from the previous visit and record their stop dates or confirm if they are still continuing.
- Record nonstudy vaccines and concomitant medications as described in [Section 5.8.1](#).
- Conduct a targeted physical examination, including vital signs if appropriate, evaluating any clinically significant abnormalities based on history and the participant's self-reported symptoms or complaints since the last visit. Abnormal results, including those that indicate worsening of medical history conditions, must be recorded on source documents and the AE CRF (with recording of time relative to vaccination) as appropriate.

- Measure and record the subject's oral temperature.
- Ensure that none of the temporary delay criteria are met ([Section 4.5](#)).
- Collect a blood sample of approximately 20 mL for immunogenicity testing ([Section 7.2](#)).
- An appropriately qualified **blinded** member of the site staff should evaluate the previous injection site for any ongoing reactions from the previous vaccination. If there is no persisting injection site reaction from the previous vaccine administration, the investigational product should be administered by the **unblinded** administrator. If an injection site reaction is still present, investigational product should be administered by intramuscular injection in the upper deltoid muscle of the opposite arm by the **unblinded** administrator.
- The unblinded vaccine administrator updates the investigational product accountability records.
- Blinded study staff will observe the subject for at least 30 minutes after investigational product administration for any acute reactions. Any AEs noted during the observation period should be recorded as immediate AEs.
- Record and report AEs and SAEs (relative to the time of vaccination) as described in [Section 8](#) and the [Schedule of Activities](#).

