### 9.3. Safety Analysis

The safety population will include all subjects who receive at least 1 dose of an investigational product. For the safety analysis, subjects will be analyzed according to the investigational product received. For each stage (original planned stage [first 3 vaccinations] and extension stage [fourth vaccination]), all safety data will be analyzed separately for each planned dosing regimen (Days 1, 8, and 30 or Months 0, 1, and 6).

AEs will be categorized according to MedDRA and will be summarized by vaccine group. All summaries of AEs will show the number and percentage of subjects experiencing at least 1 event and the number of events for each vaccine group.

The proportion of subjects reporting local reactions at the injection site and systemic events on any day within the 7- to 14-day period after vaccination will be descriptively summarized by vaccine group. Severities of local reactions and systemic events reported after each vaccination will also be descriptively summarized by vaccine group. Two-sided exact 95% CIs will be presented with the proportions.

CCI

.

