#### **9.4.1. First Interim Analysis**

The first interim analysis is planned for the study when Month 2 data are available from all continuing subjects. All available immunogenicity and safety data will be included in this analysis.

The objective of the first analysis is to determine the suitability of the Day 1, 8, and 30 regimen for further study.

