## **3.6. Study Conduct**

### **3.6.1. E-Diary Completion**

An e-diary will be considered transmitted if any data for the 3 local reactions, the 7 systemic events (including fever, vomiting, diarrhea, headache, fatigue, new or worsening muscle pain, and new or worsening joint pain), or use of antipyretics/pain medication to treat symptoms are present on any day. If all data are missing for all items on the e-diary for all days following vaccination (all 7 days following the first vaccination on the Day 1, 8, and 30 regimen, all 14 days following the first vaccination on the Month 0, 1, and 6 regimen, all 14 days following the second vaccination for both regimens, and all 14 days following the third vaccination for both regimens), then the e-diary will be considered not transmitted.

For transmitted e-diaries, the following variables will be defined: “Day 1,” “Day 2,” “Day 3,” “Day 4,” “Day 5,” “Day 6,” “Day 7,” “Day 8,” “Day 9,” “Day 10,” “Day 11,” “Day 12,” “Day 13,” “Day 14” (“Day 8” to “Day 14” only applicable to after Dose 2, Dose 3 on the Day 1, 8, and 30 regimen, and after each dose on the Month 0, 1, and 6 regimen), and Dose 4 in the extension stage in both regimens, “Day 1 – Day 7” (for after the first vaccination on the Day 1, 8, and 30 regimen), and “Day 1 – Day 14” (for after the second and the third vaccinations on the Day 1, 8, and 30 regimen, and after each vaccination on the Month 0, 1, and 6 regimen, and fourth vaccination in the extension stage of both regimens).

An e-diary will be considered completed if all expected data for all days are available (ie, not missing) and data are valid. Otherwise, the e-diary will be considered incomplete. For any given day, an e-diary will be considered complete if all expected data are available.

For completed e-diaries, the following variables will be defined for: “Day 1,” “Day 2,” “Day 3,” “Day 4,” “Day 5,” “Day 6,” “Day 7,” “Day 8,” “Day 9,” “Day 10,” “Day 11,” “Day 12,” “Day 13,” “Day 14” (“Day 8” to “Day 14” only applicable to after Dose 2, Dose 3 and Dose 4 in the extension stage of both regimens), “Day 1 – Day 7” (for after the first vaccination on the Day 1, 8, and 30 regimen), and “Day 1 – Day 14” (for after the second and the third vaccinations on the Day 1, 8, and 30 regimen, and after each vaccination on the Month 0, 1, and 6 regimen, and fourth vaccination in the extension stage of both regimens).

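### Cumulative reactogenicity is summarised over 7 days after Dose 1 of the Day 1, 8, 30 regimen and over 14 days after every other dose, with no cumulative summary over a common window, so some dose-to-dose and between-regimen readings may partly reflect window length.

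*SAP*

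**What the plan says.** SAP 6.5.2 defines the window for the cumulative reactogenicity variables as "X = 7 days after the first vaccination on the Day 1, 8 and 30 regimen, and X = 14 after all other vaccinations". SAP 3.5.3.1 and 3.5.3.2 build presence on any day and maximum severity on those windows, for local reactions and systemic events alike. The summary after any vaccination in the original stage pools the same unequal windows.

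Protocol 9.3 is consistent with this but does not standardise it: it counts events "on any day within the 7- to 14-day period after vaccination". The short first window has a design reason, because in the Day regimen Dose 2 is due "7 to 11 Days After Visit 1".

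For the later doses the two regimens match. SAP 3.6.1 refers to "all 14 days following the second vaccination for both regimens" and "all 14 days following the third vaccination for both regimens". In SAP 3.6.1 and 5.3.2, a Day 1 to Day 7 cumulative variable exists only for Dose 1 of the Day regimen.

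Two other outputs are relevant. SAP 3.5.3 derives presence of each reaction or event, and presence at Grade 3 or worse, on each single diary day. SAP 6.5.2 says the derived endpoints will be summarised and adds descriptive statistics for onset day.

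**The concern.** A percentage of subjects with at least one event cannot fall as the window lengthens, and it rises if any subject first reports an event in the added days. Headache, fatigue, and muscle or joint pain are likely to have some background occurrence at ages 65 to 85. A column that reads lower at Dose 1 than at Dose 2 of the Day regimen may therefore look like increasing reactogenicity when it partly reflects 7 days set against 14.

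The pattern across doses will attract attention. The Protocol Summary reports that an earlier study of a different formulation, on the same schedule, stopped vaccinating after "7 cases of Grade 3 injection site erythema among 162 subjects receiving the second vaccination at Day 8". The first interim analysis here reviews all available safety data, and Protocol 9.4.1 states its purpose: "The objective of the first analysis is to determine the suitability of the Day 1, 8, and 30 regimen for further study". At Month 2 the Month regimen has received only Doses 1 and 2, so Dose 1, where the windows differ, is one of just two dose-level comparisons available.

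No hypothesis is tested (SAP 5.1), so the displayed percentages and their intervals are themselves the evidence.

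**Working it through.** **Stated figures.** The documents give no figure for the effect of window length. The nearest safety figure is in Protocol 9.1: a 0.84 probability of seeing at least one AE at a true rate of 1.0% with 183 subjects. It reproduces: 1 - (1 - 0.01)^183 = 0.841.

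**Inputs from the documents.** Windows of 7, 14 and 14 days in the Day regimen and 14, 14 and 14 in the Month regimen; 183 subjects per vaccine group; about 61 placebo subjects per regimen.

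**Assumed inputs.** P7, the proportion with an event on Days 1-7, taken as 10% or 20%. f, the share of subjects affected by Day 14 whose first event falls on Days 8-14, taken as 0 to 30%. The documents give neither.

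**Diary days in the any-vaccination summary.** Day regimen: 7 + 14 + 14 = 35. Month regimen: 3 x 14 = 42.

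**Excess at a single dose, with no true difference on Days 1-7.** P14 = P7 / (1 - f), and the excess is P14 - P7. Under a constant daily hazard, P14 = 1 - (1 - P7)^2.

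| | f = 0 | 5% | 10% | 20% | 30% | Constant hazard |
|---|---|---|---|---|---|---|
| P7 = 10%: excess, points | 0 | 0.5 | 1.1 | 2.5 | 4.3 | 9 |
| P7 = 20%: excess, points | 0 | 1.1 | 2.2 | 5.0 | 8.6 | 16 |

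For example, at P7 = 20% and f = 30%, P14 = 0.20 / 0.70 = 28.6%. Under constant hazard, P14 = 1 - 0.80^2 = 36%.

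**Same calculation from a daily onset rate r.** With 1 - (1 - r)^7 and 1 - (1 - r)^14, assumed rates of 1%, 2% and 3% give 6.8% and 13.1%, 13.2% and 24.6%, and 19.2% and 34.7%. The excess is about 6 to 16 points.

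**Scale.** With 37 of 183 subjects (20.2%), the exact 95% interval is 14.7% to 26.8%, a half-width of about 6 points. At P7 = 20% the excess is below this at f = 20% and above it at f = 30%.

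**Any-vaccination gap, assuming independent doses with equal rates.** Day regimen: 1 - (1 - P7)(1 - P14)^2. Month regimen: 1 - (1 - P14)^3. At P7 = 20% the gap is 1.3 points at f = 10%, 2.8 at f = 20% and 4.4 at f = 30%. Under constant hazard it is 73.8% - 67.2% = 6.6 points.

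**Can the planned outputs recover a Days 1-7 figure?** Not in general.
- Daily percentages cannot be added, because one subject may report on several days.
- The single-day variables cover each reaction or event and Grade 3 or worse. They do not cover any local reaction, any systemic event, or the full maximum-severity scale.
- Onset statistics default to n, mean, median, SD, minimum and maximum (SAP 5.2), which do not count subjects with onset by Day 7.

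**Where window length contributes nothing.** Between regimens at Dose 2 and at Dose 3, both windows are 14 days. Within a regimen, vaccine and placebo share a window at every dose.

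**The case against.** A reader might infer that every difference between regimens is contaminated, or that an artefact is already shown. The documents support neither. Dose 2 on Day 8, the dose behind the earlier safety stop, is compared with Dose 2 of the Month regimen over equal windows. The excess can be zero, because the share of first reactions on Days 8-14 is not given.

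The case against goes further. Days 1 to 7 can be read day by day for every dose. If the latest onset day for a reaction is 7 or earlier, its 7-day and 14-day proportions coincide; otherwise the Days 8-14 daily counts bound the excess. A background-driven rise would also show in the placebo column. No dose-to-dose or between-regimen estimate is planned, and every window is stated openly. Grade 3 erythema has its own review rule by dose and regimen (Protocol 7.1.2). The review committee may ask for further analyses (SAP 7.2), and its charter is not available here. The Phase 1 statement that "the frequency and severity of local reactions did not increase with increasing dose level or number of doses for any of the dose groups" describes a completed study, not an analysis planned in this one.

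Most of this stands, and it limits the point to modest importance. It does not close the gap. One late first onset pushes the maximum past Day 7 without saying how many subjects are involved. Placebo gives only an imprecise correction: 12 of 61 (19.7%) has an exact 95% interval of 10.6% to 31.8%, and risk differences are planned only for tier 1 and tier 2 AEs, not for reactogenicity. The Phase 1 statement does show that reactions by dose number are something the sponsor reports.

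**Conclusion.** The unequal windows are real, and no cumulative presence or maximum-severity summary over a common window is planned. Window length may therefore inflate Doses 2 and 3 relative to Dose 1 in the Day regimen. It may also make the Day regimen look milder than the Month regimen at Dose 1 and in the any-vaccination figure. Other contrasts are untouched.

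The size is unknown. The range of 0 to about 9 points, or 16 under constant hazard, rests on an assumed 20% Days 1-7 rate and an assumed timing of first events. The upper end fits background systemic complaints better than local reactions, which probably start early; for those the effect is probably small. These figures should not be carried over to Grade 3 erythema. The 7-day diary after Dose 1 follows from the schedule and is not at fault. This is a free improvement of modest importance in a descriptive study.

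**What to change.** In SAP 3.5.3 and 6.5.2, add the following over Days 1-7 after every dose in both regimens: presence of each local reaction and systemic event, presence of any local reaction and any systemic event, and maximum severity. Add a version of the any-vaccination summary that uses Days 1-7 after each dose. State that any dose-to-dose or between-regimen comparison will rest on these tables. Keep the planned 14-day summaries, which describe later reactions.

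The cost is SAP wording and one further set of tables. Days 1-7 are already collected at every dose, so neither the diary schedule nor any other procedure changes.
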